## **9.2. Clinical Laboratory Evaluations**

The local clinical laboratory data (i.e. chemistry, hematology) will be graded according to CTCAE v5.0, for applicable tests. Grade 0 will be assigned for values that fall outside of the grading criteria.

Actual value and change from baseline value will be descriptively summarized by visit and treatment group for each laboratory test. Shift tables in toxicity grades from baseline to each scheduled post-baseline visit will be provided as well for the laboratory tests with gradings. A shift table from baseline to the worst post-baseline grade will be provided for the laboratory tests with gradings. Unscheduled assessments will be considered as well when identifying the worst post-baseline grade.

Listings of laboratory data will be provided.

## **9.3. Vital Sign Measurements**

Vital sign measurements include height (cm), weight (kg), temperature (°C), blood pressure (mmHg) and pulse rate (beats/min). Descriptive statistics of baseline, actual value and change from baseline at each time point will be provided by visit and treatment group for vital signs except for height which will only be summarized at baseline.

A listing of vital sign data will be provided.

## **9.4. Electrocardiogram**

ECG parameters include heart rate (beats/min), PR interval (msec), QRS duration (msec) and QTc interval (msec). The ECG results will be interpreted by investigator and recorded as: normal, abnormal not clinically significant, or abnormal clinically significant on eCRF pages. Descriptive statistics of continuous ECG parameters and shift summary of ECG result interpretation from baseline will be provided by visit.

A listing of ECG data will be provided.

## **9.5. LVEF Evaluation**

Actual value and change from baseline in LVEF (%) will be summarized by scheduled visit and treatment group.

A listing of LVEF data will be provided.

## **9.6. ECOG Performance Status**

The ECOG performance status will be summarized as a categorical variable by visit and treatment group. Descriptive summary table for change from baseline in ECOG performance grade will also be provided by visit.

A listing of ECOG performance grade will be provided.

## 10. Other Analyses

All the summaries will be performed using the Safety set.

### 10.1. Immunologic Assessments

Collection of blood samples for humoral immunity will be performed for all patients as scheduled in the [Schedule of Study Procedures](#).

[REDACTED]

Listings of humoral immunogenicity data will be provided.

Analyses of cellular immunogenicity data are conducted by Imugene and is documented separately.

#### 10.1.1. Time-adjusted Area Under Curve (AUC) of Her-2-specific Antibodies

[REDACTED]

Scatter plot to observe the relationship of time-adjusted AUC of Her-2-specific antibody from Baseline to Day 84 with change in tumor size from baseline to Day 84 will be presented.

#### **10.2. Serum and Biochemical Markers of Tumor Progression**

Analyses of serum and biochemical markers of tumor progression data are conducted by Imugene and is documented separately.

#### **10.3. In-Vitro Inhibition of Tumor Cell Growth**

Analyses of Her-2-specific antibodies (IgG) inhibition of in-vitro tumor cell growth data are conducted by Imugene and is documented separately.

#### **10.4. Intra-tumor Analysis**

Analyses of intra-tumor analysis data are conducted by Imugene and is documented separately.

## **11.Independent Data Monitoring Committee**

An IDMC will regularly monitor the data from this Phase 2 study. The IDMC review meeting will be conducted after 8, 16 and 24 PFS events occur and at intervals of no less than once per year. The purpose of the data review is for safety evaluation. Further details of the IDMC review will be provided in the IDMC charter and separate analysis plan.

## 12. Secondary Endpoint Analysis

After 24 PFS events have been realized, the final analysis of PFS will be performed, which will also include an OS interim superiority analyses. A failure to meet statistical criterion for PFS will not prevent the final assessment of survival.

As for the final analysis of PFS, and OS interim analysis, in addition to the efficacy analysis on endpoints PFS and OS, it also includes:

- Summary of treatment discontinuation and study discontinuation;
- Summary of the demographics, baseline disease characteristics;
- Summary of study treatment exposure;
- Summary and analysis of other efficacy endpoints including TTP, DCR, ORR, DOR, CTS;
- Overview summary of TEAEs, summaries of all TEAEs by CTCAE grade, treatment-related TEAEs, TEAEs leading to treatment discontinuation, Injection site reaction TEAEs, serious TEAEs and TEAEs leading to death;
- Summary of local laboratory tests, ECG tests, LVEF and ECOG performance grade;
- Summary of AUC and time-adjusted AUC for Her-2-specific antibody and correlation of the Her-2-specific antibody with change in tumor size, PFS and OS;

The same analysis methods will be used as full analysis described in previous sections of this SAP.

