## 1. Introduction

This Statistical Analysis Plan (SAP) describes the analyses and data presentations for Imugene Limited protocol IMU.ACS.001 “HERIZON: A Phase 1b/2 Open-label Study of IMU-131 HER2/neu Peptide Vaccine Plus Standard of Care Chemotherapy with Randomization in Phase 2 in Patients with HER2/neu Overexpressing Metastatic or Advanced Adenocarcinoma of the Stomach or Gastroesophageal Junction”, which was amended on 17 Feb 2021 (Amendment No. 3). The protocol has a 2-part design: Phase 1b and Phase 2, and this SAP is specifically for the Phase 2 study. It contains definitions of analysis populations, derived variables and statistical methods for the analysis of efficacy, safety and immunogenicity.

The following analyses are planned in this study.

- Periodic safety analyses for Independent Data Monitoring Committee (IDMC) safety reviews
- The final analysis of progression free survival (PFS) after 24 evaluable PFS events have been realized
- The final analysis of overall survival (OS) after 24 deaths (at the end of study)

This SAP will only cover the secondary endpoint analysis at clinical cutoff of 24 evaluable PFS events and the primary endpoint analysis of OS at clinical cutoff of 24 OS events. The detail analyses for IDMC safety review is specified in the IDMC charter.

Throughout this SAP, the treatment group will be referred to as the IMU-131 plus chemotherapy group and chemotherapy alone group. The purpose of the SAP is to ensure the credibility of the study findings by pre-specifying the statistical approaches to any data analysis prior to database lock. This SAP will be finalized and signed prior to the clinical database lock for the final PFS analysis at 24 evaluable progression events. Any significant changes after final PFS analysis and prior to final database lock for primary endpoint OS analysis after 24 deaths will be documented in Final SAP Amendment.

All statistical analyses detailed in this plan will be conducted using SAS® 9.4 or later (SAS Institute Inc., Cary, North Carolina).

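### SAP Section 12 adds an interim OS superiority analysis that Section 1 does not list, and Section 1 leaves the primary OS analysis open to amendment after that look

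*SAP*

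**What the plan says.** SAP Section 3.2 and the protocol name OS as the primary efficacy endpoint of Phase 2.

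SAP Section 1 lists three planned analyses:

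- recurring safety looks for the IDMC;
- one PFS analysis, triggered by the 24th evaluable event;
- one OS analysis, triggered by the 24th death, which closes the study.

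Its scope sentence has the same structure: "This SAP will only cover the secondary endpoint analysis at clinical cutoff of 24 evaluable PFS events and the primary endpoint analysis of OS", the latter at 24 OS events. No interim OS analysis is named.

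Section 1 also looks past the PFS cut. "Any significant changes after final PFS analysis" and before the final lock for OS are to be recorded in a final SAP amendment. The visible text does not say which kinds of change are allowed.

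SAP Section 12 describes the analysis at 24 PFS events as the final PFS analysis, "which will also include an OS interim superiority analyses". It says that missing the PFS criterion does not prevent the final survival assessment, and it closes with "The same analysis methods will be used as full analysis described in previous sections of this SAP".

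Section 12 gives no number of deaths, boundary or remaining alpha for the OS look, and no pointer to where these stand. The visible text of Protocol Sections 10.4.2 and 10.7.2 mentions no interim OS analysis.

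**The concern.** There are two linked issues.

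First, a superiority analysis is a test, not a summary. Section 12 therefore has the primary endpoint tested at the PFS cut and again at 24 deaths, while Section 1 describes one OS analysis. Someone working from Section 1 alone would not know that the first look exists. If no boundary applies to it, the overall type I error for OS exceeds the nominal level.

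Second, because OS results are part of the PFS-cut output, the period in which Section 1 allows significant changes begins after the comparative OS data have been analysed. The trial is open-label, and SAP Section 4.4 keeps only the central radiography reviewers blinded. A change to the test, strata, population or censoring of the primary analysis made in that period could be influenced by the result, or could not be shown to be free of that influence. This does not depend on whether an interim boundary exists.

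**Working it through.** **Step 1: what can be reproduced.** The plan's own figure is 24 deaths. It cannot be reproduced, because the visible text gives no hazard ratio, alpha, sidedness or power for OS. SAP Section 4.3 and the opening of Protocol Section 10.7.2 are withheld.

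**Step 2: count the OS analyses.**

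| Source | At 24 PFS events | At 24 deaths |
|---|---|---|
| SAP Section 1 (list and scope) | PFS | OS |
| SAP Section 12 | PFS, plus interim OS superiority | final OS still follows |

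Section 1 gives one OS analysis and Section 12 implies two.

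**Step 3: how early the look would fall.** The plan does not give the number of deaths at the 24th PFS event. It was simulated from 36 patients and 22 months of uniform accrual (SAP Section 3.1), with exponential PFS and post-progression survival. The medians are assumptions: 4-7 months for PFS and 8-13.5 months for OS. The result is about 12-21 deaths. The information fraction is t = deaths at the look / 24, which gives about 0.50-0.86.

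**Step 4: overall type I error if both looks use the same unadjusted level.** This condition is assumed, not stated in the plan. Under the null, the two log-rank statistics Z1 and Z2 are approximately bivariate normal with correlation √t. With critical value c = z(1-α) at both looks:

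overall error = 1 - P(Z1 ≤ c, Z2 ≤ c)

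The correlation is √0.50 = 0.707, √0.80 = 0.894 and √0.86 = 0.927.

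| One-sided level | c | t = 0.50 | t = 0.80 | t = 0.86 |
|---|---|---|---|---|
| 0.025 | 1.960 | 0.042 | 0.035 | 0.034 |
| 0.05 | 1.645 | 0.080 | 0.069 | 0.066 |
| 0.10 | 1.282 | 0.153 | 0.132 | 0.127 |

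Widening the assumption to 10-22 deaths (t = 0.417-0.917) gives 0.043-0.032, 0.083-0.062 and 0.158-0.120.

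**Step 5: effect of a stringent interim level.** Testing the interim at one-sided 0.001 (c1 = 3.090) and the final at the full level gives 1 - P(Z1 ≤ 3.090, Z2 ≤ c). For t = 0.50-0.86 this is at most 0.0253, 0.0502 and 0.1001 for the three levels. The final level is essentially unchanged.

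**The case against.** The strongest reply is that the error-rate argument depends on text that is not public. SAP Section 4.3 is withheld. Sections 8.2.8.2 and 8.2.8.3 refer to an inferential analysis in Section 8.1 that the visible text of 8.1 does not contain. Section 12 itself mentions a statistical criterion whose value is not shown. A boundary could sit in any of these places, and the sentence carrying over the methods of previous sections could bring it into the interim look. This stands. A reader might infer from Section 12 that alpha is not controlled, but the documents do not support that, because using the same methods is not the same as using the same critical value.

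A reader might also see a conflict with Section 11, where "The purpose of the data review is for safety evaluation". There is none. Section 12 does not give the OS look to the IDMC, and a safety-only IDMC is compatible with an OS analysis run by the sponsor at the PFS cut.

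Third, the change clause is not unrestricted: changes go into a SAP amendment before the final lock. That also stands. But documenting a change does not prevent it from being made with knowledge of the OS result.

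Fourth, Section 1 does name the PFS-cut analysis, so it omits a component rather than excluding it, and this is a 36-patient Phase 2 whose final OS assessment goes ahead whatever the PFS result. This makes the mismatch milder. It does not remove it, because the omitted component is a test of the primary endpoint.

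**Conclusion.** The point holds in a limited form. Two things are established from visible text. Section 12 includes an interim superiority analysis of the primary endpoint that Section 1 does not list. And Section 1 lets the plan be significantly amended after the analysis in which that OS comparison is made.

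Inflation of the type I error is conditional. It requires that both looks use the same unadjusted level, which the public text neither confirms nor rules out. Under that assumption, with an information fraction of 0.50-0.86, one-sided 0.025 becomes about 0.034-0.042, 0.05 becomes 0.066-0.080, and 0.10 becomes 0.127-0.153. The fraction rests on assumed PFS and OS medians, and no alpha or sidedness is visible. If a boundary is already specified, these figures do not apply, and what remains is the inconsistency between the sections and the open amendment window.

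**What to change.** 1. In SAP Section 1, state that the primary OS analysis (test, strata, population and censoring) is frozen at the PFS database lock, and that later changes are reported only as sensitivity analyses.
2. In SAP Section 1, list the OS look at the 24-PFS-event cut among the planned analyses.
3. In SAP Section 12, cite the interim boundary and the remaining final alpha if they are already specified. If none exists, choose one of two options. Either make the OS output at the PFS cut descriptive (estimate and confidence interval, no superiority claim), so that the 24-death analysis keeps its full alpha. Or use a stringent boundary such as one-sided 0.001, which leaves the final level essentially unchanged. An O'Brien-Fleming boundary would also hold the level: for overall one-sided 0.025 with 12, 16 or 20 deaths at the look, the interim levels are 0.0026, 0.0071 or 0.0133 and the final levels 0.0240, 0.0226 or 0.0215.

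The cost is SAP wording only. The downside is less freedom to amend the OS analysis and, if no boundary exists today, no early OS claim at the nominal level.

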## 15.Appendices

### 15.1. Appendix 1: Schedule of Study Procedures – Phase 2

	Screen	Baseline	Week 2 K (+/- 3d)	Week 3 (+/- 3d)	Week 5 K (+/- 3d)	Week 6 (+/- 3d)	Week 9 (+/- 7d)	Week 11 K (+/- 7d)	Week 12 (+/- 7d)	Week 15 (+/- 7d)	Week 18 (+/- 7d)	Week 20 K (+/- 7d)	EoT Visit P (+/- 7d)	Post-treatment FU Visit (+/- 7d)
Study Days	-21d to -1d	0	14	21	35	42	63	77	84 repeat every 84 days (+/- 7d)	105	126 repeat every 84 days (+/- 7d)	140 repeat every 63 days (+/- 7d)	At least 28 (+/- 7) days after last dose	Every 42 days after EoT
Survival/anti-cancer treatment														X
IMU-131 Vaccination		X	X		X			X				X		
Chemotherapy F		X		X		X	X		X	X				
Informed Consent	X													
Demographics and prior medications	X													
Medical History	X													
Cancer History	X													
Physical Exam O	X	X		X		X	X		X	X	X		X	
Weight and vital signs (temp, BP, pulse) L	X	X	X	X	X	X	X	X	X	X	X	X	X	
Height	X													
ECOG performance status	X	X							X				X	
Radiographic Assessment E		X				X			X		X			X G
Cardiac Assessment H	X								X				X	
Tumor biopsy I	X								X J				X J	
Urine Pregnancy Test A	X	X	X	X	X	X	X	X	X	X	X	X	X	
HIV, Hepatitis M	X													
Hematology, Chemistry M	X	X		X		X	X		X	X	X		X	
Exploratory endpoint labs B		X							X				X	
Immunology – humoral C		X		X		X	X		X		X		X	
Immunology - cellular C		X							X				X	

	Screen	Baseline	Week 2 K (+/- 3d)	Week 3 (+/- 3d)	Week 5 K (+/- 3d)	Week 6 (+/- 3d)	Week 9 (+/- 7d)	Week 11 K (+/- 7d)	Week 12 (+/- 7d)	Week 15 (+/- 7d)	Week 18 (+/- 7d)	Week 20 K (+/- 7d)	EoT Visit P (+/- 7d)	Post-treatment FU Visit (+/- 7d)
Study Days	-21d to -1d	0	14	21	35	42	63	77	84 repeat every 84 days (+/- 7d)	105	126 repeat every 84 days (+/- 7d)	140 repeat every 63 days (+/- 7d)	At least 28 (+/- 7) days after last dose	Every 42 days after EoT
Concomitant Medications	X	X	X	X	X	X	X	X	X	X	X	X	X	
Concomitant Procedures	X	X	X	X	X	X	X	X	X	X	X	X	X	
Adverse Events		X	X	X	X	X	X	X	X	X	X	X	X	

A Negative urine pregnancy test required for women of childbearing potential at screening and prior to each vaccination. If positive urine test vaccination may be delayed until negative BHCG blood test.

B A 1 x 10 mL whole blood sample to assess vaccine-specific cytokine levels and in-vitro inhibition of tumor cell growth will be obtained from each patient at Days 0, 84 then every 84 days and at EoT visit.

C 1 x 10 mL (i.e. 1 tube) whole blood sample for humoral immunity at Baseline, Days 21, 42, 63, 84, 126 then every 42 days and EoT visit and 5 x 8 mL blood samples at Baseline, Days 84 then every 84 days and EoT visit for cellular immunity. To be taken prior to vaccination at Baseline visit.

D Chemotherapy will be administered as a concomitant therapy to all patients as a 21-day regimen consisting of: cisplatin by intravenous administration at 80 mg/m^2 on the first day of each cycle and either 5-FU, 4000 mg/m^2 CIV (administered as 1000 mg/m^2/day as continuous infusion for 96 hours on days 1 to 4 of each cycle) or capecitabine for 14 days at 2000 mg/m^2/day, orally (administered as 1000 mg/m^2 twice daily morning and evening for a total of 2000 mg/m^2/day on days 1 to 14 of each cycle), or capecitabine for 14 days at 2000 mg/m^2/day, orally (administered as 1000 mg/m^2 twice daily morning and evening for a total of 2000 mg/m^2/day on days 1 to 14 of each cycle) and oxaliplatin, by intravenous administration at 130 mg/m^2 on Day 1 of each cycle. Body weight to be measured and body surface area to be calculated based on weight and baseline height at the start of each 21-day chemotherapy cycle. Chemotherapy continues until ceased by the investigator as clinically indicated for the care of the patient. To document compliance while away from the clinic, patients will record capecitabine treatment in a patient diary.

E Radiographic assessment to occur within 14 days prior to Baseline Visit, then at Days 42, 84, 126 every 42 days thereafter. Radiographic assessment continues until disease progression according to RECIST 1.1 response criteria irrespective of whether patient has withdrawn from the study.

F Chemotherapy continues for up to 6 cycles until disease progression or until ceased by the investigator as clinically indicated for the care of the patient, whichever occurs first.

G Radiographic assessment according to RECIST 1.1 response criteria at post-treatment follow-up visit only for patients withdrawn from the study prior to disease progression.

H Cardiac assessment will be based on assessment of medical history, physical examination, 12-lead ECG results and evaluation LVEF by echocardiography or MUGA scan at Screening, Days 84 then every 84 days and at EoT visit.

I No tumor biopsy is required if a previous pathology result or archival tissue is available confirming HER2/neu expression consistent with Inclusion Criteria #6.

J Optional Day 84 and post-progression tumor biopsy (which may be provided at any time during the post-treatment follow-up period).

K Visit only for 'IMU-131 plus chemotherapy' group.

L Record temperate 30min (+/- 10mins) after each IMU-131 vaccination.

M Local laboratory testing. Safety lab samples can be drawn up to 72 hours before any on-study clinic visit.

O A targeted, symptom directed physical examination may be performed at visits occurring after the Baseline Visit.

P When progressive disease or withdrawal from study has been confirmed, EoT visit will be conducted at least 28 Days (+/- 7) after last dose of study medication. AEs to be checked at least 28 days after last study treatment per [Section 9.2: Reporting Period](#).

## 15.2. Appendix 2: Imputation Rules for Medication/Adverse Event Date

Missing onset dates (where UK and UKN indicate unknown or missing day and month respectively)

[figure not shown]
- UK-MMM-YYYY:
  - If the month and year are different from the month and year of the first dose of study drug, assume 01-MMM-YYYY.
  - If the month and year are the same as the first dose of study drug month and year, and the end date (after any imputation) is on or after the first dose of study drug, then assume the date of the first dose of study drug.
  - If the month and year are the same as the first dose of study drug month, and year and the end date (after any imputation) is prior to the first dose of study drug, then assume the end date for the onset date.
- DD-UKN-YYYY/UK-UKN-YYYY:
  - If the year is different from the year of first dose of study drug, assume 01-JAN-YYYY of the collected year.
  - If the year is the same as the first dose of study drug year, and the end date (after any imputation) is on or after the first dose of study drug, then assume the date of the first dose of study drug.
  - If the year is the same as the first dose of study drug, and the end date (after any imputation) is prior to the first dose of study drug, then assume the end date for the onset date.

Missing end dates (where UK and UKN indicate unknown or missing day and month respectively):

- UK-MMM-YYYY: Assume the last day of the month;
- DD-UKN-YYYY/UK-UKN-YYYY: Assume 31-DEC-YYYY

All the imputed end date will not be later than the last day on study.

Client:	Imugene Limited
Protocol Number:	IMU.ACS.001
Document Description:	Final Statistical Analysis Plan
SAP Title:	HERIZON: A Phase 1b/2 Open-label Study of IMU-131 HER2/neu Peptide Vaccine Plus Standard of Care Chemotherapy with Randomization in Phase 2 in Patients with HER2/neu Overexpressing Metastatic or Advanced Adenocarcinoma of the Stomach or Gastroesophageal Junction
SAP Version Number:	5.0
Effective Date:	12 July 2022

